6.7.2. DLT for Phase I

A DLT is defined as one or more events occurring during cycle 1. For more details, see Section 2.1.1.5.

A summary table of DLTs by treatment group occurring during cycle 1 will be provided, presenting the number and percentage of patients with DLTs, the number of DTLs per patient, and the type of DLTs in patients of phase 1 from the safety DLT Evaluable Analysis Set.

A by-patient listing of DLTs that occur during cycle 1 is planned by treatment group and for all patients from the DLT Evaluable Analysis Set during phase I of this trial. Patients will be grouped by the treatment group to which they are originally assigned, including those who may receive subsequent treatment at a lower or higher dose level.

Patients with and without DLTs from the DLT Evaluable Analysis will be plotted in a graph with dose level on the vertical axis and patient number (patient id sorted in the order in which they received the first dose) on the horizontal axis.

MTD will initially be estimated as the next suggested dose level from the CRM model described above based on all data in the DLT analysis set. This corresponds to the dose level with a posterior probability of DLT that comes closest to the toxicity level of 0.15.

Final MTD is determined by the DMC and the safety group, as other safety data than the DLTs may be relevant

6.7.3. Adverse Events

An AE is any untoward medical occurrence in a patient administered a pharmaceutical product which does not necessarily have a causal relationship with the treatment.

An AE can, therefore, be any unfavorable and unintended sign (including an abnormal laboratory finding), symptom, or disease temporally associated with the use of a product, whether or not considered related to the product.

An AE includes:

- A clinically significant worsening of a concomitant illness.
- A laboratory abnormality which is clinically significant, i.e. an abnormality that suggests a disease and/or organ toxicity and is of a severity that requires active management. Active management includes interventional treatment or further investigations, for example change of medicine dose or more frequent follow-up due to the abnormality.

Each AE is to be classified by the Investigator as either serious or non-serious. This classification of the seriousness of the AE determines the reporting procedures to be followed. An AE that meets one or more of the following criteria/outcomes is classified as serious:

- Is fatal or life-threatening
- Requires inpatient hospitalization or prolongation of existing hospitalization
- Results in persistent or significant disability/incapacity
- Is a congenital anomaly/birth defect
- Medically important event

All AEs recorded on the eCRF will be coded using the MedDRA dictionary [23.1].

The overall observation period for AEs will be divided into 3 parts:

- Pre-treatment period: From the day of the patient's informed consent to the day before the first dose of Hu3F8-BsAb
- On-treatment period: From the day of the first dose of Hu3F8-BsAb to 30 days after the last dose of Hu3F8-BsAb
- Post-treatment period: From 31 days after the last dose of Hu3F8-BsAb and thereafter

If dates are incomplete in a way that clear assignment to pre-, on-, post-treatment period cannot be made, the respective data will be assigned to the on-treatment period.

AE will be classified as Treatment–Emergent AEs (TEAEs) as follows:

• TEAEs are either events with start date and time after initiation of treatment, or events with start date and time prior to the start of the on-treatment period whose severity worsens on or after initiation of treatment.

Some AE of the on-treatment period will not be TEAE if they occur on the day of the first treatment but before the time of the first treatment. If start time is incomplete in a way that clear assignment as TEAE/Non-TEAE cannot be made, the AE will be considered as TEAE.

In addition, if AE starts (date/time) before first dose and grade is greater than 1 and stop (date date/time) is after first dose or missing, then this AE will be considered as a TEAE.

- Treatment-Emergent Serious AEs (TESAEs) will be defined as TEAEs regarded by the investigator as Serious = "Yes".
- The relationship between a TEAE and Hu3F8-BsAb is assessed as definite, probable, possible, or not related. A Hu3F8-BsAb-related TEAE will be defined as a TEAE considered by the investigator as definitely, possibly, or probably related to Hu3F8-BsAb or with unknown / missing relationship to Hu3F8-BsAb.
- Assessment of AE severity / intensity will be based on the National Cancer Institute-Common Terminology Criteria for AEs (NCI-CTCAE⁹, version 4.0) apart from CRS events that will be graded using Lee grading system.. Severe TEAEs are defined as TEAEs assessed as being "Severe (Grade 3) / Grade 4 / Grade 5" in intensity.
- •
- TEAEs leading to discontinuation of treatment are defined as TEAEs where "Action Taken with Study Treatment" is indicated as "Treatment discontinued".

Adverse events will be summarized by default descriptive summary statistics for categorical variables for the Safety Analysis Set by treatment group (phase I) and cancer type (phase 2) and overall as follows:

- An overview of TEAEs with onset during the pre-treatment or the treatment period including the number and percentage of patients with at least one of each mentioned TEAE type as well as the number of events:
 - Any TEAE
 - Leading to discontinuation of trial treatment
 - Leading to death
 - Grade 1 severity (mild)
 - Grade 2 severity (moderate)
 - Grade 3 severity (severe)
 - Grade 4 severity (life-threatening or disabling)
 - Grade 5 severity (death related to TEAE)
 - Missing severity grade
 - Any treatment related TEAE
 - Leading to discontinuation of trial treatment
 - Leading to death
 - Any serious TEAE
 - Leading to discontinuation of trial treatment
 - Leading to death
 - Any serious treatment related TEAE
 - Leading to discontinuation of trial treatment
 - Leading to death
- For TEAs with onset during the pre-treatment or the treatment period the number and percentage of patients reporting each TEAE and the count of number of events will be summarized by SOC and PT for the following types of TEAEs:
 - o TEAEs
 - TEAEs Leading to Discontinuation of Trial Treatment
 - TEAEs Leading to Death
 - TEAE Related to COVID-19 if applicable
 - Grade 3, 4 or 5 TEAE
 - Infusion Related TEAE (defined as all related TEAEs occurring on the day of infusion after initiation of infusion if times are not missing; otherwise, if time is missing, it will correspond to all related TEAEs occurring on the day of infusion)
 - o Grade 3, 4 or 5 Infusion Related TEAE
 - o Trial Treatment Related TEAEs
 - Grade 3, 4 or 5 Related TEAEs
 - o Treatment Related TEAEs Leading to Discontinuation of Trial Treatment
 - Treatment related TEAEs Leading to Death
 - Serious TEAEs
 - Serious TEAEs of grade 3 or higher
 - Serious TEAEs Leading to Discontinuation of Trial Treatment
 - Serious TEAEs Leading to Death
 - Related Serious TEAEs of grade 3 or higher

- Treatment Related Serious TEAEs
- Treatment Related Serious TEAEs Leading to Discontinuation of Trial Treatment
- Treatment Related Serious TEAEs Leading to Death
- The number and percentage of patients who died will be summarized by the primary reason of death

In the above summaries, patients with more than one TEAE within a particular SOC are counted only once for that SOC. Similarly, patients with more than one TEAE within a particular PT are counted only once for that PT.

Summaries by SOCs and PTs will be sorted by SOCs by their Internationally Agreed Order (MedDRA 23.1) and PTs within SOC by descending order of total incidence. Where counts preferred terms tie, PTs will be sorted alphabetically.

No statistical comparisons of AEs between treatment groups will be performed.

All AE data will be listed separately and Pre-treatment period, the On-Treatment period and the Post-treatment period. Treatment-emergence status will be flagged. The listings will present the relative start and stop day of the AE calculated relative to the first dose of treatment and will be presented for those patients who received at least one dose of treatment. If the AE is "Ongoing" it will be indicated as such in the listings and the relative stop day will not be calculated. Only original dates will be presented in the listings even though the relative day may be based on an imputed date.

In addition, the following listings will be presented combined for all three periods (a column with onset period (pre-treatment, on-treatment, post-treatment) will be displayed):

- Listing of Deaths
- Listing of Serious TEAEs
- Listing of AEs Leading to Interruption of Trial Treatment
- Listing of AEs Leading to Discontinuation of Trial Treatment
- Listing of AE related to COVID-19, if applicable
- Listing of non-TEAEs

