17.2.4 Adverse Event Reporting Period

17.2.4.1 Non-Serious Events

Non-serious AEs should be reported from the day of first IMP (Hu3F8 BsAb) administration until 30 days after the last IMP administration. Non-serious AEs occurring between signing the ICF and the first IMP administration must be recorded as medical history.

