17.2.4.2 Serious Adverse Events

Serious AEs should be reported from signing the ICF until 30 days after the last IMP administration.

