17.2.5.4 Severity

For all AEs, apart from cytokine release syndrome, the Investigator will use the Common Terminology Criteria for Adverse Events (CTCAE) version *4.0* to describe the severity of the AE. AEs of cytokine release syndrome will be graded using the CRS revised grading system by Lee et al.⁹¹ described in Table 8 in Section 11.3. If the severity changes over the course of the event, the grade assigned by the Investigator should be the most severe, that occurred during the AE period.

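### SAP 6.7.3 has conflicting rules for adverse events that start before first dose, and the broadest one counts unchanged or improving pre-treatment SAEs of Grade 2 or higher as treatment-emergent

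*SAP*

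**What the plan says.** SAP Section 6.7.3 (Adverse Events) contains three statements about events that begin before treatment.

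- **Worsening clause.** Besides new events, TEAEs include "events with start date and time prior to the start of the on-treatment period whose severity worsens on or after initiation of treatment".
- **Day 1 sentence.** An event on the first treatment day that precedes the time of the first treatment is not a TEAE. If the start time is too incomplete to decide, it is treated as one.
- **Carry-over sentence.** Introduced as an addition, it reads "if AE starts (date/time) before first dose and grade is greater than 1 and stop (date date/time) is after first dose or missing", with the consequence "then this AE will be considered as a TEAE". It has no condition on change in grade.

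The same section then says that "Treatment-Emergent Serious AEs (TESAEs) will be defined as TEAEs regarded by the investigator as Serious", and the TEAE overview and the tables by SOC and PT expressly include events with pre-treatment onset.

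Three protocol rules decide which records these sentences meet:

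- Section 17.2.4.1: "Non-serious AEs occurring between signing the ICF and the first IMP administration must be recorded as medical history".
- Section 17.2.4.2: "Serious AEs should be reported from signing the ICF until 30 days after the last IMP administration".
- Section 17.2.5.4, when severity changes over time: "the grade assigned by the Investigator should be the most severe, that occurred during the AE period".

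**The concern.** One section gives incompatible answers for the same record. Take an SAE that starts after consent, is Grade 3, is still open at first dose and never changes. It fails the test "whose severity worsens on or after initiation of treatment", so under the worsening clause it is not a TEAE. Under the carry-over sentence it is. A Day 1 event before the infusion is likewise excluded by one sentence and included by another if it is above Grade 1 and still open.

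The programmer will probably apply the broadest rule, because it is worded as an addition. Serious events that predate the drug and did not change then sit in the dose-level summaries of serious and severe TEAEs. Safety is part of the Phase I primary objective. Under SAP 6.7.8.2 the monitoring committee receives the Phase I safety analyses before advising on the MTD and RP2D, and SAP 6.7.2 says safety data other than DLTs may bear on the final MTD. A summary table that mixes carried-over events with new ones is harder to read for that purpose, above all when a dose level holds one patient.

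**Working it through.** The documents give no figure to reproduce here, so the check is a comparison of rules.

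**Step 1. Inputs.** For an event with onset before first dose, let g0 be the highest grade before first dose (1 to 4) and g the single recorded worst grade (g0 to 5, Protocol 17.2.5.4). The stop date falls before first dose, after it, or is missing. An event that stopped before first dose is flagged by neither rule, so only the two open states matter.

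**Step 2. Rules.**
- Worsening clause: TEAE if g > g0.
- Carry-over sentence: TEAE if g > 1.

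**Step 3. Counts of logical profiles.**
- Pairs (g0, g): 5 + 4 + 3 + 2 = 14. With two open stop states: 14 × 2 = 28.
- Worsening clause: (4 + 3 + 2 + 1) × 2 = 20.
- Carry-over sentence: all pairs except (1, 1), so (14 − 1) × 2 = 26.
- Flagged by the worsening clause but not by the carry-over sentence: 0, because a grade that rises must reach at least 2.
- Flagged by the carry-over sentence only: 26 − 20 = 6. These are the unchanged Grade 2, 3 and 4 events, each with stop after dose or missing.
- Flagged by neither: 28 − 26 = 2, the unchanged Grade 1 events.

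These are counts of cases, not of expected patients. They show that the carry-over sentence absorbs the worsening clause entirely, so the clause has no effect on any table. Improving events are caught too: an SAE that peaked at Grade 3 before dosing and was lower but still open at first dose has g = g0 = 3 and is recorded as Grade 3.

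**Step 4. Which events.** Non-serious events before first dose go to medical history and SAEs are recorded from consent, so the carry-over sentence meets almost only SAEs. The qualifier is for Day 1: Protocol 17.2.4.1 also starts non-serious reporting on the day of first administration, so a non-serious event earlier that day could be entered as an AE.

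**Step 5. Which tables.**

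| Output | Unchanged pre-dose SAE, Grade 2 or higher, still open |
|---|---|
| Any TEAE; serious TEAE | Included |
| Grade 3-5 TEAE | Included if Grade 3 or above |
| Treatment-related TEAE | Included only if rated at least possibly related, or if the relationship is unknown or missing |
| CRM-phase DLT, CRM, initial MTD estimate | Not affected: SAP 2.1.1.5 and 6.7.2 use DLT data, not the TEAE flag |

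**Step 6. Size.** The tables count patients with at least one event, so one carried-over SAE adds at most one patient, and none if that patient has another event in the same row. The maximum per event is 1/1 = 100% at a level with one patient, 1/3 = 33% with three, and 1/30 = 3.3 percentage points over 30 Phase I patients. The number k of affected patients is not in the documents. As an assumed range only, k = 0, 1, 2, 3 gives at most 0, 3.3, 6.7 and 10.0 points over 30.

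**The case against.** The best defence is that the carry-over sentence is a deliberate conservative convention. With only the worst grade on the record, a single entry cannot show whether an event straddling first dose worsened before or after it. The carry-over rule can be computed from that entry and misses no worsened event, as Step 3 confirms. Simply deleting it could lose events that did worsen. That stands, and it shapes the fix. The SAP, however, neither gives this reason nor labels the rule, and it leaves the two conflicting statements in place.

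A reader might infer that these SAEs are counted as toxicity of the drug. The documents do not support that. Treatment emergence is about timing; attribution is recorded separately, must be given from the first report (Protocol 17.2.5.6), and governs the related-event tables.

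A reader might also infer that dose escalation or the Phase I primary endpoint is biased. It is not: the endpoint is DLT in cycle 1, and the CRM-phase rule rests on attribution.

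The carry-over is also traceable. AE data are listed by period, the serious-TEAE listing has an onset-period column, and no statistical comparison of AEs is planned. This limits the harm, but no such split is specified for the summary tables.

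Finally, entry criteria exclude most existing major-organ toxicity of Grade 3 or above and active life-threatening infection, so the number of affected events may well be zero. An assumption such as 1 to 3 of 30 has no support in the documents.

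**Conclusion.** The conflict is real and can be read directly from SAP 6.7.3: the carry-over sentence makes the worsening clause redundant and contradicts the Day 1 sentence. Its practical effect is to classify open pre-treatment SAEs of Grade 2 or higher as treatment-emergent even when unchanged or improving. Compared with the worsening definition, the affected summary counts can only rise.

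The size is modest and unknown: at most one patient per event in a dose-level count, possibly none in the whole trial. The conclusion assumes that sites follow the protocol's recording rules and that the SAP is programmed as written. It does not extend to drug attribution, apart from unknown or missing relationships, or to DLTs, the CRM or the initial MTD estimate. The content of the monitoring committee's packages during the trial is left to a charter and shells that are not available here. The point is worth correcting because the change is cheap and dose-level denominators are small.

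**What to change.** Replace the three statements in SAP 6.7.3 with one rule, cut at the date and time of first dose so that Day 1 events are covered:

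1. A pre-dose event is a TEAE only if its grade rises on or after first dose. Show this either by a new AE record dated at the worsening or by recording the grade at first dose.
2. Where the timing of the worst grade cannot be established, for example in records already entered, keep the grade-above-1 rule as a fallback and label it as conservative.
3. In the summary tables, show TEAEs with pre-dose onset separately from new-onset TEAEs. Unchanged pre-dose events remain in the pre-treatment listing.

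The cost is a revision of SAP wording, one eCRF completion instruction, a few site queries for SAEs open at first dose, and one extra table row or column. The SAP cites a final eCRF version and patients had already been treated, so the fallback is needed to avoid losing events that truly worsened.

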6.7.4. Laboratory Evaluations

Data for the following hematology, serum chemistry, and urinalysis parameters recorded in the eCRF are to be measured at the scheduled visits / time points indicated in Table 2 and Table 3 (see section 2.1.3).

Table 7 Laboratory Tests

Hematology	Serum Chemistry	Blood Urinalysis
Test (SI unit)	Test (SI unit)	
Red Blood Cell Count (RBC)	• ALT (U/L)	• Color
$(10^{12}/L)$	• AST (U/L)	 Specific Gravity
• Hemoglobin (g/L)	 Total Bilirubin (mmol/L) 	• pH
• Hematocrit (%)	• Total Protein (g/L)	Protein/ Albumin
White Blood Cell Count (WBC)	• Phosphate (mmol/L)	• Glucose
$(10^{9}/L)$	 Alkaline phosphatase (U/L) 	• Ketones
• Differential WBC (10 ⁹ /L and %)	• Albumin (g/L)	• Bilirubin
 Neutrophils 	• Creatinine (mmol/L)	• Urobilinogen
 Lymphocytes 	 Blood Urea Nitrogen (BUN) 	 Leucocyte Esterase
• Eosinophils	(mmol/L)	• Nitrate
• Basophils	• Potassium (mmol/L)	• RBC
\circ Monocytes	• Sodium (mmol/L)	• WBC
• Platelet count $(10^{7}L)$	 Magnesium (mmol/L) 	 Epithelial Cells
• Mean Corpuscular Volume	• Chloride (mmol/L)	Small Round Cells
(MCV)	 Carbon Dioxide (Bicarbonate) 	• Casts
• Mean Corpuscular Hemoglobin	(mmol/L)	 Pathological Casts
(MCI)	• Ferritin (nmol/L)	• Sperm
• Mean Corpuscular Hemoglobin Concentration (MCHC)	• C-reactive Proteins (mg/L)	• Bacteria
• Pad call Distribution Width	 Lactate Dehydrogenase (ukat/L) 	• Yeast
(PDW)		
 Mean Corpuscular Volume (MCV) Mean Corpuscular Hemoglobin (MCH) Mean Corpuscular Hemoglobin Concentration (MCHC) Red cell Distribution Width (RDW) 	 • Magnestan (nmol/L) • Chloride (mmol/L) • Carbon Dioxide (Bicarbonate) (mmol/L) • Ferritin (nmol/L) • C-reactive Proteins (mg/L) • Lactate Dehydrogenase (ukat/L) 	 Small Round Cells Casts Pathological Casts Sperm Bacteria Yeast

In accordance with the baseline value definition in Section 5.1.2, the absolute and percentage change from baseline will be derived as follows:

Absolute change (unit) = (post-baseline value – baseline value)

Percentage change from baseline = [(post-baseline value– baseline value) / baseline value] \times 100

All laboratory data will be reported in SI units. All quantitative laboratory test values at each assessed timepoint will be compared with the relevant reference range in SI units and categorized as:

- Low: Below the lower limit of the reference range.
- Normal: Within the reference range (upper and lower limits included).
- High: Above the upper limit of the reference range.

For analysis purposes, values preceded by a "<" (i.e. those below the limits of quantification) will be considered equal to the half of the Lower Limit Of The Quantification (LLOQ/2). Those preceded by a ">" sign (i.e. those above the limits of quantification) will be considered equal to the upper limit of quantification.

Laboratory values will be assigned toxicity grades, when available*, using criteria based on the NCI CTCAE version 4.03^9 .

Parameters whose grade can be derived are the followings:

- Hematology
 - Hemoglobin (Low)
 - Hemoglobin (High)
 - WBC (Low)
 - WBC (High)
 - Neutrophils (absolute) (Low)
 - Lymphocytes (absolute) (Low)
 - Lymphocytes (absolute) (High)
 - Platelet (Low)
- Serum chemistry
 - \circ Sodium (Low)
 - Sodium (High)
 - o Potassium (Low)
 - Potassium (High)
 - Magnesium (Low)
 - Magnesium (High)
 - Creatinine (High)
 - Total Bilirubin (High)
 - ALT (High)
 - AST (High)
 - ALP (High)
 - Albumin (Low)

Laboratory data will be summarized by default descriptive summary statistics for continuous and categorical variables for the Safety Analysis Set by treatment group and overall as follows:

- Observed values and absolute change from baseline at each assessed timepoint for each standard continuous laboratory parameter;
- Number and percentage of patients with categorized shift (low, normal and high) values relative to the reference range at baseline compared to each post-baseline value for hematology and serum chemistry (for phase II only);
- Number and percentage of patients with worst NCI-CTCAE toxicity values;
- Number and percentage of patients with categorized shift NCI-CTCAE toxicity values at baseline compared to worst post-baseline timepoint.

Listings of all clinical laboratory data including derived percentage change from baseline will be provided for the Safety Analysis Set. Within each listing, laboratory values outside the

normal ranges will be flagged as either high or low and NCI-CTCAE grading will be provided for applicable laboratory assessments.

In addition, the following figures will be displayed:

- Longitudinal plot of laboratory parameters in patient with at least one abnormal value (Three different plot symbols will indicate whether the values were Low, Normal or High)
- Baseline and post baseline plot of laboratory parameters per cycle and per week

